The research activities involve a two-arm prospective RCT enrolling a sample of 600 AMSM with the aim of maintaining a randomized sample of approximately 500 online-recruited AMSM (13-18), assuming 15-20% attrition. After consent and completion of the online baseline survey, AMSM are randomized to either the control or experimental condition (Intervention, n=300; Control, n=300). Participants in the control arm will receive access to only the resource locator function of iReach, allowing them to search for local resources. Participants recruited nationally will receive a list of national resources. Participants in the experimental arm will receive access to all iReach functions, including life skills education, goal setting, local/national resource directory, a discussion forum related to life skills and goal setting, and the ability to link to a Peer Mentor through the VSee video-chat function. After consent and a baseline survey, AMSM are randomized to either the attention control or intervention condition. Self-completed study assessments are conducted online every three months across the intervention and attention-control follow-up time points, with a total follow-up period of 12 months for participants initially randomized into the intervention group, and 15 months for participants initially randomized into the control group. In months 12 to 15, we will make the intervention accessible to AMSM in the attention-control condition. The primary outcomes are cognitive (e.g., HIV prevention attitudes, norms, self-efficacy, behavioral intentions); behavioral outcomes are secondary (e.g., condom use, HIV testing, PrEP use). The proposed study design thus tests the impact of an e-delivered life skills intervention with an embedded video-chat peer motivational interviewing function on cognitive and behavioral HIV-related outcomes on a large (n=600) sample of AMSM.

The study is funded for approximately 5 years (Project Period: 07/28/2016 to 02/28/2021). Once consented, participants randomized into the intervention group will be active in the study for 12 months. Participants randomized into the control group will be active in the study for 15 months.

METHODS:

1. Study Instruments:

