
intervention was to navigate and its technical responsiveness; and perceived usefulness reflects how the intervention was perceived by participants to impact their health behaviors. Scores range from 1 (Strongly Disagree/Very Unlikely) to 7 (Strongly Agree/Very Likely). Intervention Exposure, Fidelity & Dosage: We will measure intervention exposure using paradata from the intervention, including counts of user sessions, session lengths, pages visited and functions utilized. For the VSee peer counseling component, we will record the number and duration of VSee sessions, as well as the domains covered in these sessions. We will also include MITI fidelity scores across the sessions. This information will assist in examining whether intervention dosage influences the overall efficacy of the intervention, as well as inform the Secondary Aim regarding cost analysis and wider implementation and scalability.

2. Group Modifications:

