The research activities involve a two-arm prospective RCT enrolling a sample of 600 AMSM with the aim of maintaining a randomized sample of approximately 500 online-recruited AMSM, assuming 15-20% attrition. After consent and completion of the baseline survey, AMSM are randomized to either the control or experimental condition (Intervention, n=300; Control, n=300). Participants in the control arm will receive access to only the resource locator function of iReach, allowing them to search for local/national resources. Participants in the experimental arm will receive access to all iReach functions, including life skills education, goal setting, a discussion forum related to life skills and goal setting, local/national resource directory, and the ability to link to a peer mentor through the VSee video-chat function. Self-completed study assessments are conducted online every three months across the intervention and attention-control follow-up time points, with a total follow-up period of 12 months. At the end of the trial, we will make the intervention accessible to AMSM in the attention-control condition for a 3 month period, followed by an additional follow-up assessment at month 15. The primary outcomes are cognitive (e.g., HIV prevention attitudes, norms, self-efficacy, behavioral intentions); behavioral outcomes are secondary (e.g., condom use, HIV testing, PrEP use). The proposed study design thus tests the impact of an e-delivered life skills intervention with an embedded video-chat peer motivational interviewing function on cognitive and behavioral HIV-related outcomes on a large (n=600) sample of AMSM.

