Attention Control Condition: Participants randomized to the control condition will receive access only to the Resource Locator embedded within iReach. While the provision of a service locator is a form (albeit weak) of an intervention and may decrease our ability to detect intervention effects, we felt that withholding referrals to services would be unethical given AMSM's vulnerability to HIV and STIs. By providing the existing testing site locator only, we will still be able to test the effect of iReach (i.e., user-tailored content focused on life skills + peer mentor counseling through VSee). Participants initially randomized into the control condition will receive three months of access to the full intervention after they have completed 12 months in the control condition.

Additionally, during months 12 to 15 of participation, we will test whether incentivization of app engagement has any effect on participant utilization of intervention features. Participants initially randomized to the control condition, upon completing 12 months in the attention control condition and receiving three months access to the full intervention, will be informed that they can earn an additional \$40 reward for earning badges totaling 25 points in the iReach app (see image of point system below). See page 14 of this document for a description of iReach badges. Participants will be able to choose which badges they want to pursue, and therefore will be able to choose which intervention actions they complete in order to earn the incentive. Badges are set up to reward incremental use of app features (e.g. badge 1 = read one page, badge 2 = read five pages, etc.). We have developed the point system and chosen the target of 25 points so as to reward moderate use of the app, use which requires meaningful but achievable use. Participants who reach the 25 point target during their three months of full intervention access will earn an additional \$40 Amazon gift card, paid after the completion of the 15 month survey (or timing out of the survey window).

2. Data Collection:

Data will be collected from participants through web surveys at baseline, month 3, month 6, month 9, and month 12 (and month 15 for participants initially randomized into the control condition). For participants who engage in peer mentoring sessions with peer mentors, information about the session will be documented at the time of the session.

3. Genetic Testing:

Not applicable.

4. Use of Deception:

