
5. Protected Health Information

The following PHI identifiers will be collected in this study:

- Name
- Street address, city, county, precinct, zip code, and equivalent geocodes
- All elements of dates (except year) for dates directly related to an individual and all ages over 89
- Telephone numbers
- Electronic mail addresses
- Web addresses (URLs)
- Internet IP addresses
- Biometric identifiers, including finger and voice prints
- Full face photographic images and any comparable images
- Any other unique identifying number, characteristic, or code

6. Compensation and Incentivization:

Compensation for completing the baseline, the 12-month follow-up survey, and the 15-month follow-up survey (for participants initially randomized into the control condition) will be \$30 per assessment, whereas the 3, 6, and 9-month follow-ups will be \$25 each since they are shorter in length.. This compensation is small enough to avoid undue influence, yet sufficiently substantial to compensate for time and effort, and promote retention. Participants will be eligible to receive \$135 - \$165 compensation for completing surveys, depending on which group they are randomly assigned to, if they complete all assessments.

Additionally, participants randomized into the control condition will be eligible to earn a \$40 incentive for intervention use during their three month period of full intervention access from months 12 to 15. Participants earn this incentive for collecting iReach badges totaling 25 points, markers of completing the various actions described in the Experimental Group description above. Given the minimal risks associated with intervention use, this incentive does not constitute an undue influence. Participants randomized into the intervention group will not be eligible for this incentive.

All compensation and incentives will be paid as Amazon gift cards. Payment for the baseline survey will be sent once participants have completed the survey and have responded to the email containing their iReach WebApp login credentials. All subsequent compensation Amazon cards will be sent after the participant completes the associated survey. The incentive will be sent to participants who earn it after the 15 month survey. Participants who earn the incentive but do not complete the 15 month survey will receive the incentive after they time out of the 15 month survey window.

7. Data and Safety Monitoring:

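### The month 12-15 test of the $40 incentive has no concurrent or randomised comparison group, and the plan names no comparator or analysis for it

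*Protocol*

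**What the plan says.** The Protocol (Study Procedures, 1. Detailed Description, Attention Control Condition) sets out an add-on for months 12 to 15: "we will test whether incentivization of app engagement has any effect on participant utilization of intervention features". The people told of the $40 reward are described as "Participants initially randomized to the control condition, upon completing 12 months in the attention control condition and receiving three months access to the full intervention". They earn it by collecting badges worth 25 points.

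The Protocol's section 6, Compensation and Incentivization, repeats that the control arm can earn an "incentive for intervention use during their three month period of full intervention access from months 12 to 15" and adds: "Participants randomized into the intervention group will not be eligible for this incentive".

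Three other statements bear on who could be compared with whom:

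- Study Design: "Once consented, participants randomized into the intervention group will be active in the study for 12 months".
- Detailed Description, opening paragraph: "we will make the intervention accessible to AMSM in the attention-control condition for a 3 month period".
- Study Instruments, on exposure and dosage: "We will measure intervention exposure using paradata from the intervention, including counts of user sessions, session lengths, pages visited and functions utilized".

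Neither document describes a second random allocation, an offer limited to some controls, or a date on which the offer began. The models in the Protocol's Statistical Analysis section and the SAP's Efficacy Analyses section use baseline and four follow-ups, which ends at month 12. The SAP does not mention the incentive.

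**The concern.** Asking whether an incentive has any effect on use is a causal question. It needs people with the same access, at the same stage, who were not offered the incentive. The plan gives the offer to every crossover control and has no such group in months 12 to 15.

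What is at stake is the conclusion of the add-on itself. If crossover controls use the app heavily, the $40 may get the credit when the cause is something else. If they use it little, the incentive may be judged useless when a year in the study has dulled interest. Either error could carry into decisions on how to roll out the app. With no outcome, comparator or model fixed in advance, the choice of comparison would also be made after the data are seen.

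**Working it through.** The plan gives no sample size, effect size or analysis for this test, so there is no figure to reproduce. The check has three parts.

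**1. Who has full access without the offer, and when**

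| Group | Months 0-12 | Months 12-15 |
|---|---|---|
| Intervention arm | Full app, no offer | No longer in the study |
| Control arm | Resource locator only | Full app, all offered $40 |

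The number with full access and no offer in months 12 to 15 is therefore 0. Taken alone, the add-on yields a single-group estimate. With 250 crossover controls and an assumed 50% reaching 25 points, the 95% half-width is 1.96 × √(0.25/250) = 0.062, or about 6.2 points. That describes use but says nothing about the effect of the offer.

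**2. The only available comparator**

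This is the intervention arm in its first three months of access (n = 300, from "Intervention, n=300; Control, n=300") against 250 crossover controls (the SAP's expected complete data per arm, Randomization and Blinding). The detectable standardised difference at two-sided 0.05 and 80% power is

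(1.960 + 0.842) × √(1/300 + 1/250) = 2.8016 × 0.0856 = 0.24.

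Precision is not the problem; bias is. Suppose the incentive does nothing, 50% of the intervention arm reach some use threshold (assumed), and other causes raise that rate among crossover controls. The chance of a significant result is Φ[(δ − 1.96·SE₀)/SE₁], with SE₀ pooled and SE₁ unpooled:

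| Difference not due to the incentive | Chance of p < 0.05 |
|---|---|
| 5 points | 21% |
| 10 points | 65% |
| 15 points | 94.5% |

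The documents give neither the base rate nor the size of such differences, so these figures only illustrate the risk.

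**3. What a randomised offer could detect**

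The number crossing over is not stated. The assumed range runs from 240 (300 × 0.80, the 20% loss the plan allows for) through 250 to 300 (no loss). With a 1:1 split into n per group, d = 2.8016 × √(2/n):

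| Crossing over | n per group | d | Points, from 20% | Points, from 50% |
|---|---|---|---|---|
| 240 | 120 | 0.362 | 16.2 | 17.7 |
| 250 | 125 | 0.354 | 15.8 | 17.4 |
| 300 | 150 | 0.323 | 14.3 | 15.9 |

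The last two columns solve the two-proportion power formula above for 80%. The 20% and 50% no-offer rates are assumptions.

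**The case against.** A reader might infer that the test has no comparison group of any kind. The documents do not support that. The intervention arm is barred from the incentive, has full access and has its use logged, and it came from the same 1:1 allocation. It is a usable, if non-concurrent, comparator.

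Some of the biases can also be reduced. The intervention arm's data can be cut to its first three months, matching the length of crossover access. Age can be adjusted for. Selection by retention should not be overstated: access follows completion of 12 months in the control condition, but nothing ties it to completing the month-12 survey, and the SAP's Missing Data section lets participants continue after missed surveys. Some selection through withdrawal remains possible.

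All of this stands, and none of it rescues the causal reading. Crossover controls meet the full app after a year of study contact and locator use, and about a year later in calendar time relative to their own enrolment. The intervention arm meets it at the start. Cutting the window does not remove that difference, and no unincentivised group shares the controls' history, so adjustment has nothing to work with.

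It is also fair that the add-on is minor. It is not among the four aims or the SAP endpoints, and much of the defect is the word *test* together with a missing analysis description.

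**Conclusion.** The concern holds in a limited form. In months 12 to 15 there is no concurrent or randomised comparison group for the incentive, and neither document names a comparator, an outcome or a model. The one unincentivised full-access group is the intervention arm in an earlier period, and a contrast with it confounds the incentive with time in study, prior locator use, calendar time and possible withdrawal. The effect of the incentive cannot be isolated under the plan as written.

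A reader might also infer that the trial's efficacy comparison is compromised. It is not: the offer begins after the month-12 assessment, and the efficacy models stop there. The point is worth correcting but of low severity.

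The conclusion that the effect cannot be isolated rests on the text alone. The detectable differences rest on an assumed 240 to 300 controls crossing over and, for proportions, on assumed no-offer rates.

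**What to change.** **Preferred.** At month 12, randomise crossover controls 1:1 to be told of the $40 offer or not, with identical app access. Compare use of intervention features over months 12 to 15 by assigned group. Take the main outcome from the app paradata already collected, and define it in advance. Keep reaching 25 points as a supporting outcome only: the Badges paragraph shows that badges also reward completing surveys, and points are the very thing being paid for. Add the outcome and model to the SAP, and amend the Compensation and Incentivization text that makes the whole control arm eligible.

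**Cost.** A short amendment and a second allocation step. Incentive spending falls by up to half: with 250 controls, the most payable drops from 250 × $40 = $10,000 to 125 × $40 = $5,000. About half the controls would not receive the offer. Word of it may also spread through the discussion forum, which would dilute the contrast.

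**If all controls must be offered it.** Replace the claim of a test with an exploratory descriptive report. Name the intervention arm's first three months of access as a non-concurrent comparator, specify the paradata outcome, list the differences that cannot be removed, and draw no causal conclusion. This costs only a change of wording and a paragraph in the SAP.

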Not applicable.

5. Statistical Analysis:

Descriptive statistics of the psychosocial and demographic characteristics of the participants will be described for all and by intervention group. These will be compared between treatment groups using t-tests or Wilcoxon rank sum tests for continuous variables and chi-square tests for categorical variables. In addition, we will use the general framework of generalized linear mixed models (GLMM) to test for intervention effects over time. Note that some of our outcomes are binary, some count and some continuous traits and thus need to be treated differently. The general form of the GLMM will be $\mu_{ij} = \beta_0 + \beta_1 \text{cov} + \beta_2 \text{Time} + \beta_3 \text{InterventionGroup} + \beta_4 \text{Group} \times \text{Time}$, where μ_{ij} is the mean response corresponding to subject i at Time j (baseline and 4 follow-ups) with the appropriate link function (identity for continuous outcome, logit for binary outcome and natural log for count outcomes); Group = 1 if the i -th subject is in the intervention group and 0 if the i -th subject is in the attention-control group. The interaction coefficients β_4 (Group \times Time) are of interest here, measuring the difference in the rate of change in outcomes across the two treatment groups over time. The subject-specific random intercepts β_0i are assumed to be normally distributed with a common variance and they account for within-person correlation. We will also explore if we need a subject specific random-slope corresponding to visit in the above model. Maximum likelihood estimation will be used for fixed effect parameters. Models will be compared according to information criterion like AIC, BIC. For some binary outcomes like HIV testing, we will perform an aggregate analysis after collapsing across the repeated measures using simple logistic regression comparing whether the probability of having tested at least once over the entire FU period is different across treatment groups, after adjusting for baseline values. To ensure robustness, we will also apply an exchangeable working correlation structure to its corresponding generalized estimating equation (GEE) model. We will also conduct exploratory regression analyses to examine differences based on social determinants of interest: age group, race/ethnicity, and rurality. These regressions will be run with group assignment and the social determinant variables of interest in the models, controlling for region. Interactions between group assignment and these social determinants will be tested to explore potential group-specific moderators of treatment effect. Given our focus on disparities, we also intend to examine mean differences across sub-groups of interest (e.g., race/ethnicity, developmental age group, urban vs. suburban vs. rural). For example, assuming we used a fixed effects ANOVA model with main effects and interactions by race and intervention condition, we would be able to detect any interaction effect size f of .18 in cross-sectional analyses at 80% power using a two-sided significance level of .05. Similar interaction effect sizes are obtained for developmental age (i.e., early (ages 13-14) vs. middle (ages 15-16) vs. late (ages 17-18) adolescence) and rurality (i.e., urban vs. sub-urban vs. rural). Secondary Analyses: Building on our GLMM framework employed for Aim 2, we will examine whether there are intervention effects in the socioecological factors (e.g., LGBT discrimination; HIV stigma) and life skills components (e.g., personal competence; identity development) associated with our outcomes. The regressions will be run with group assignment only in the model, as well as controlling for participants socio-demographic characteristics, psychological distress, and intervention-related process data (e.g., frequency of use, acceptability). In addition, we will test whether these relationships vary as a function of AMSMs varying engagement with the intervention (e.g., dose analysis; intervention acceptability, frequency of site log-ins; time spent on sites and modules; number and length of VSee sessions used). Interactions between group assignment and these characteristics will be tested to explore potential moderators of treatment effect. Recognizing that social determinants operate beyond the individual-level, we will use HLM to test how regional characteristics influence AMSMs outcomes. HLM allows us to take into account that participants are nested within regions, and examine whether regional characteristics are associated with individual-level outcomes. We will link individual and regional level data using participants residential address at enrollment. Some participants may be residentially unstable and/or would not want to give their exact location. We will estimate a two-level model to account for individual and regional variation.

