Eligible individuals must (1) have been assigned a male sex at birth and identify as male at the time of enrollment into the study (cis-gender male), (2) be between the ages of 13 and 18 years (inclusive), (3) speak and read English, (4) report same-sex attractions and/or behaviors, (5) have access to the Internet, (6) live in one of the zip codes at least partially contained in the 109 counties included in the four regions selected for this trial, and (7) self-report as HIV-negative at time of enrollment.

Randomization and Blinding

Participants are randomized on a 1:1 basis using a stratified randomization by race and region. AMSM will be randomized to one of two arms, with 300 randomized to each arm (complete data on 250 AMSM per arm, allowing for attrition of 50 AMSM per arm).

Study Assessments

The proposed domains mirror the theoretical framework informing our intervention. We include a summary of the primary and secondary outcomes, key intervention mechanisms of change, and potential covariates. Assessments will not take more than 25 minutes to complete. We have taken several steps to ensure that the assessments are brief and developmentally appropriate. First, AMSM will not answer all listed constructs at every assessment. Identity-related constructs, for example, will be measured at 6-month intervals, whereas other constructs (e.g., comfort discussing sexuality) will be assessed at each follow-up. Second, consistent with best practices that we have used in prior HIV studies with pediatric and adolescent populations^{142,256}, we will use gate-keeping questions to decide whether participants should receive other probes within a domain. For example, a participant who has yet to become sexually active would receive cognitive assessments focused on HIV risk and awareness (e.g., attitudes, norms), but would not receive questions regarding behavioral intentions to engage in HIV prevention in next 3 months (e.g., HIV testing, PrEP) or questions regarding sexual risk behaviors (e.g., sexual behavior, HIV testing, PrEP use). Similarly, at each assessment, AMSM with no lifetime substance use will not be asked about additional substance use questions. Among sexually active participants, gatekeeping also provides opportunities to regulate how detailed the assessments will be.

Domain	Assessment time					
	Baseline	Month 3	Month 6	Month 9	Month 12	Month 15
Primary outcomes						
HIV knowledge	X		X		X	X
Condom use/communication efficacy	X		X		X	X

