HIV/STI testing	X		X		X	X
Outcomes required for analysis						
Demographics	X		X		X	X
Patient provider communication around sexual orientation		X		X		
Stigma		X		X		
Resilience		X		X		
Psychological needs	X		X		X	X
Future life goals		X		X		
Secondary outcomes						
Internalized homonegativity	X		X		X	X
PrEP use and willingness [X		X		X	X
Sex behaviors	X		X		X	X
Substance abuse	X		X		X	X
Depression	X		X		X	X
Anxiety	X		X		X	X
Self-Esteem	X		X		X	X
Covariates						
Peer influence		X		X		
Family support		X		X		
Discrimination		X		X		
Online behaviors		X		X		
Societal reaction to sexual orientation		X		X		
Ethnicity beliefs		X		X		
Relationship history	X		X		X	X
Intervention acceptability		X				

Sample Size

Our expected sample size for analyses across both conditions is N=600 (Intervention, n=300; Control, n=300), assuming a 15-20% loss to follow-up. We estimated the minimum detectable effect sizes at 80% power, for comparisons of the two groups for the continuous primary cognitive (e.g., behavioral intentions, attitudes, norms, self-efficacy) outcomes, as well as the difference in the proportion of AMSM who report increased behavioral in the outcomes (e.g., condom use, HIV testing) to engage in HIV prevention services and behaviors in our treatment arm vs. our attention-control arm. For mean differences, our sample size calculations are based on a two-sample t-test assuming equal variance using a two-sided significance of 0.05. At 80% power, we can detect a between-arm difference of $d=0.22$ at the final follow-up. For repeated measure analyses, assuming a within-person correlation of 0.25, we would be able to detect a difference of 0.08. A less favorable within-person correlation of 0.75 allows us to detect an effect size of 0.11. For proportions, our sample size calculations are based on a two-sample test of proportions using a two-sided significance of 0.05. To have 80% power to compare active treatment to the control group, we require at least 500 participants to find a 12.5% difference between treatment and control in cross-sectional analyses. Assuming within-person correlation of 0.25, we can detect an 8.8% difference. A less favorable within-person correlation of 0.75 allows us to detect an 11.3% difference.

Timing of Analyses

Final analysis will be conducted once the desired sample size is recruited has reached and completed the last study assessment.

Analysis Populations

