Analysis tests the efficacy of the iREACH intervention as compared to a delayed intervention condition, to create positive changes in the following outcomes: *primary outcomes*: changes in confidence to engage in HIV prevention behaviors and changes in HIV knowledge and *secondary outcomes*: changes in sexual behavior and change in HIV testing behavior over the 12-month follow-up period. Descriptive statistics of the behavioral, psychosocial, and demographic characteristics of the participants will be described for all and by group (intervention and control). These will be compared between treatment groups using t-tests or Wilcoxon rank sum tests for continuous variables and chi-square tests for categorical variables. In addition, we will use the general framework of generalized linear mixed models (GLMM) to test for intervention effects over time. Note that some of our outcomes are binary, some count and some continuous traits and thus need to be treated differently. The general form of the GLMM will be $(\mu_{ij}) = \beta_{0i} + \beta_{\text{cov Covariates}_{ij}} + \beta_{\text{Time}_{j}} + \beta_{\text{Intervention Group}_i} + \beta_{\text{Group} \times \text{Time}_i}$, where μ_{ij} is the mean response corresponding to subject i at Time j (baseline and 4 follow-ups) with the appropriate link function (identity for continuous outcome, logit for binary outcome and natural log for count outcomes); Group =1 if the i -th subject is in the intervention group and 0 if the i -th subject is in the attention-control group. The interaction coefficients $\beta_{\text{Group} \times \text{Time}}$ are of interest here, measuring the difference in the rate of change in outcomes across the two treatment groups over time in the primary and secondary outcomes. Models will be compared according to information criterion like AIC, BIC. For some binary outcomes like HIV testing, we will perform an aggregate analysis after collapsing across the repeated measures using simple logistic regression comparing whether the probability of having tested at least once over the entire FU period is different across treatment groups, after adjusting for baseline values. To ensure robustness, we will also apply an exchangeable working correlation structure to its corresponding generalized estimating equation (GEE) model.

Reporting Conventions

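### The SAP's Group × Time model has a subject intercept as its only within-person term and states no standard-error type; if kept that way, its test is anti-conservative when correlation decays over time

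*Protocol*

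**What the plan says.** Both documents test efficacy with a generalized linear mixed model. The SAP (Efficacy Analyses) describes the interaction coefficients as "measuring the difference in the rate of change in outcomes across the two treatment groups over time". Its formula carries a subject subscript on the intercept and no other within-person term.

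The protocol (Study Procedures, 5. Statistical Analysis) gives the same model and two details that the SAP lacks. The random intercepts "are assumed to be normally distributed with a common variance and they account for within-person correlation". It then adds: "We will also explore if we need a subject specific random-slope corresponding to visit in the above model".

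Both documents say: "Models will be compared according to information criterion like AIC, BIC". Neither lists candidate models or gives a decision rule. Both plan one check: "To ensure robustness, we will also apply an exchangeable working correlation structure to its corresponding generalized estimating equation (GEE) model". Neither says whether its standard errors are sandwich or model-based.

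The number of visits is inconsistent. The SAP model covers "baseline and 4 follow-ups". The SAP table under Study Assessments marks the primary domains (HIV knowledge, "Condom use/communication efficacy" and HIV/STI testing) at baseline and months 6, 12 and 15, which is three visits up to month 12.

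**The concern.** A random intercept as the only within-person term forces the same correlation between every pair of visits. When visits further apart are less alike, an interaction with time is a contrast between distant visits and varies more than this model assumes. The model-based standard error is then too small and the test rejects too often under the null.

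A random slope or an unstructured covariance absorbs such decay, and sandwich standard errors protect against it. The SAP commits to none of these for the efficacy test. At stake is the nominal 5% level of the main efficacy p-values.

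**Working it through.** **Inputs from the documents**
- Two-sided alpha 0.05, 80% power, and constant within-person correlation of 0.25 or 0.75 (SAP, Sample Size).
- 250 analysed per arm (SAP, Randomization and Blinding).
- Primary-outcome visits at 0, 6 and 12 months (SAP, Study Assessments table).

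**Assumption.** The documents give no decay pattern, so a range is shown.

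**1. The plan's own repeated-measures figures.** For the average of k visits under constant correlation ρ:

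d = (1.960 + 0.842) × √(2/250) × √[(1 + (k−1)ρ)/k]

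- k = 4: d = 0.166 (ρ = 0.25) and 0.226 (ρ = 0.75). Half of these, on the Cohen f scale, is 0.083 and 0.113.
- k = 5: d = 0.158 and 0.224, so f = 0.079 and 0.112.

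The stated 0.08 and 0.11 therefore reproduce as Cohen f under one constant correlation. They concern the average over visits, not Group × Time, and say nothing about decay.

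**2. Standard error of Group × Time.** Let R be the true correlation matrix, c the centred visit times and r̄ the mean off-diagonal correlation. With complete data:

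true SE / reported SE = √[ c′Rc / ((1 − r̄) c′c) ]

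type I error = 2 × [1 − Φ(1.96 / ratio)]

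For three equally spaced visits c = (−1, 0, 1), so c′c = 2. The linear slope is then half the baseline-to-month-12 change, and the ratio is the same for that contrast if time is categorical.

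| Correlation at 6 months / 12 months | c′Rc | (1 − r̄)c′c | Ratio | Type I error |
|---|---|---|---|---|
| AR(1): 0.25 / 0.0625 | 1.875 | 1.625 | 1.074 | 6.8% |
| AR(1): 0.50 / 0.25 | 1.500 | 1.167 | 1.134 | 8.4% |
| AR(1): 0.60 / 0.36 | 1.280 | 0.960 | 1.155 | 9.0% |
| AR(1): 0.80 / 0.64 | 0.720 | 0.507 | 1.192 | 10.0% |
| Milder: 0.60 / 0.50 | 1.000 | 0.867 | 1.074 | 6.8% |
| Milder: 0.60 / 0.55 | 0.900 | 0.833 | 1.039 | 5.9% |
| Constant: 0.60 / 0.60 | 0.800 | 0.800 | 1.000 | 5.0% |

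The same test with a robust standard error stays at about 5%.

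**3. Five visits.** If the outcome were measured at 0, 3, 6, 9 and 12 months, AR(1) correlation of 0.77 per 3 months gives a ratio of 1.48 and type I error of about 19%. Over 0.25 to 0.90 per 3 months the type I error runs from 9% to 21%.

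**4. Does choosing the slope by AIC or BIC cause the error?** Null trials were simulated with 250 per arm, a continuous outcome and complete data (400 trials per scenario, Monte Carlo error about ±0.02). Correlations are AR(1) per 3 months.

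| Visits | Correlation | AIC takes slope | BIC takes slope (n = subjects) | Type I, intercept only | Type I after selection (AIC / BIC) |
|---|---|---|---|---|---|
| 3 | 0.25 | 18% | 0.5% | 0.048 | 0.048 / 0.048 |
| 3 | 0.50 | 95% | 49% | 0.070 | 0.058 / 0.062 |
| 3 | 0.75 | 100% | 100% | 0.083 | 0.048 / 0.048 |
| 5 | 0.25 | 99.8% | 98% | 0.080 | 0.055 / 0.055 |
| 5 | 0.50 | 100% | 100% | 0.158 | 0.060 / 0.060 |
| 5 | 0.75 | 100% | 100% | 0.180 | 0.055 / 0.055 |

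Selection finds the slope when the decay matters. Where it usually misses (three visits, 0.25), the reported standard error is only 2% too small. Binary and count outcomes and missing data were not simulated.

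**The case against.** The strongest reply is that the protocol already contains the remedy. It plans to explore a random slope beside an AIC/BIC comparison, and step 4 shows that such a comparison keeps the test near 5%. The SAP gives only a general form. It also omits the random-intercept distribution and the estimation method, so it reads as a shortened copy, and nothing in it withdraws the slope. A GEE is planned as well, and with sandwich standard errors it would be valid under a wrong working correlation. Finally, the only correlations in the documents are constant, and under those there is no error.

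Much of this stands. It rules out three stronger readings that a reader might reach:
- That leaving the slope to AIC or BIC itself understates the standard error. It does not; the harm needs the intercept-only model to be kept. These criteria also rank fit, not p-values, so their mention does not show that a model would be picked for its result.
- That the SAP has deliberately dropped the slope. Its silence does not establish that.
- That type I error is near 19%. That needs five visits up to month 12, which the assessment table does not give for any primary outcome.

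The reply does not close the gap. The SAP does not list the slope as a candidate. With three visits and moderate decay (0.50 per 3 months), AIC takes the slope in 95% of trials and BIC in 49%, and no rule says which governs. The GEE is a secondary check of unstated standard-error type, and its wording leaves unclear which outcomes it covers.

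**Conclusion.** This is a modest but real gap in pre-specification. As the SAP stands, an analyst could fit the intercept-only model with model-based standard errors and be following the plan. With the scheduled three visits, the type I error would then be about 7% to 10% under AR(1) decay, about 6% to 7% under milder decay, and 5% under constant correlation.

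These figures assume a continuous outcome, complete data and a decay pattern that the documents neither state nor exclude. The five-visit figures apply only if the model's visit count, rather than the assessment table, is what will happen; the two passages need reconciling.

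**What to change.** In the SAP, under Efficacy Analyses:
- Keep Group × Time as the effect of interest. Replacing it with a month-12 contrast would change the target and is a separate decision.
- For continuous outcomes, fix in advance a covariance that allows decay: unstructured, or a random slope that is always included.
- For binary and count outcomes, base inference on sandwich standard errors.
- State that the GEE uses sandwich standard errors and which outcomes it covers.
- State that AIC and BIC will not choose the covariance for the efficacy test.
- State the visits that enter each primary-outcome model, in line with the assessment table.

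The cost is SAP wording and a few more covariance parameters. With three visits, an unstructured matrix has 3 × 4/2 = 6, against 2 for the random intercept; a random slope adds 2. That is small for about 500 participants. Intervals will be slightly wider. Under AR(1) correlation of 0.75 per 3 months and three visits, the detectable 12-month difference in change is 0.293 SD, against the 0.255 SD that the intercept-only model would imply (0.293/0.255 = 1.15).
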